5.4 Risk and Control Interval

5.4.1 Definition of Observation Period, Risk and Control Intervals

Specifications for AE-specific risk and control intervals are presented in Section 4.3.

Figure 1 presents a hypothetical example of the observation period for a person that experiences a qualifying GBS event following influenza vaccination. The observation period for this person will begin on the vaccination date and extend to 90 days following vaccination, including a 42-day risk interval, and a control interval extending from day 43 to day 90 following vaccination. Risk and control intervals for individuals will vary by AE and based on the presence of any censorship criteria. AE-specific risk and control interval specifications can be referenced in Section 4.3.

Figure 1. Hypothetical Example of Observation Period, Risk and Control Interval for Individual with a Qualifying GBS Event Following Influenza Vaccination

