5.5.1 Feasibility Analysis: Statistical Power and Sample Size

A power analysis will be performed to determine when the analyses can be conducted with sufficient sample size. This will be used to establish the data cut for the analysis, which will inform the study end date. The influenza vaccination uptake distribution in the 2022-2023 influenza season will first be obtained to ensure that the vaccination cutoff date (only vaccines prior to this cutoff will be eligible for inclusion in the study) is selected to capture at least 85% of vaccinations. Then, for each AE, vaccine cutoff date, and influenza vaccine group (reference Table 3), the outcome-specific data cut date will be estimated based on (i) the length of the observation window and (ii) the outcome-specific claims delay distribution with a 90% data completeness requirement. For each AE, vaccination cutoff date and influenza vaccine group, the expected number of events during the observation window will be estimated using the AE-specific historical background rates obtained from 2021. Finally, the minimum detectable IRR will be estimated, defined as the minimum effect size that can be detected in the study based on the expected sample size at 80% power and a two-sided alpha of 0.05. To determine if there is sufficient power to conduct the analysis, for each AE, vaccination cutoff date, and influenza vaccine group, we will identify comparable IRR estimates available in the literature. These will be compared against the minimum detectable IRR estimated in the power analysis, so that the data cut date/study end date used for the analysis can balance the trade-off between being able to detect reasonable differences in incident rates and the timely initiation of analyses.

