5.5.5 Adjustments to Primary and Follow-Up Analyses

5.5.5.1 Seasonality Adjustment Analysis

Both the primary and follow-up analyses specified in Section 5.5.3 and 5.5.4 will include a seasonality adjustment, given that certain AEs included in the study demonstrate seasonal patterns in incident rates. This seasonality adjustment will adjust for changes in the baseline rate of AEs during different calendar months in the year. The baseline rate of AEs will be estimated from a similar population during the same calendar months in previous years, and subsequently included as an offset term in the regression model. For each AE, 2021 will be the comparator year used to adjust for changes in the baseline rate. Both 2020 and 2021 were considered as historical years for the seasonality adjustment; 2021 was selected as the adjustment period given that 2021 rates are more recent and thus likely more reflective of rates during the study period, and since the 2020 period has the potential to underestimate events due to changes in healthcare utilization during the early pandemic.⁽³³⁾

The Farrington and seasonality-adjusted model that will be used for the main primary and follow-up analyses is defined below.⁽²⁷⁾

$$\log(E(Y|X)) = \beta_1 * risk_interval + \log(w(t)) + \log(seasonal_risk) + strata(patient_id)$$

$$Y = AE$$

risk_interval = binary term indicating AE occurrence in risk interval

w(t) = Farrington adjusted weight

$$seasonal_risk = \frac{1}{IR_r * t} \sum_{m=1}^{12} (IR_m * t_m)$$

IR_m = daily incident rate for month *m*

IR_r = daily incident rate for reference month *r*

t_m = number of days in an interval in month *m*

$$t = \text{number of days in an interval or equivalently } t = \sum_{m=1}^{12} t_m$$

patient_id = term identifying the patient

In this model, the null and alternative hypotheses can be written as, respectively:

$$H_0: e^{\beta_1} = 1 \quad H_a: e^{\beta_1} \neq 1$$

Where e^{β_1} is the IRR for the AE in the risk interval compared to control interval adjusting for seasonality and curtailed observation time. A statistically significant coefficient at a pre-specified alpha level of 0.05 will indicate a statistically significant association between influenza vaccination and the AE.

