5.5.6 Attributable Risk (AR) Estimation

For the primary analyses and when follow-up analyses apply, the study will also estimate an adjusted AR statistic (per 100,000 vaccinations). The AR is the excess number of AE cases divided by the number of eligible beneficiaries (or eligible follow up dose-years). The number of excess AE cases due to the influenza vaccine will be derived directly from the conditional Poisson regression model, defined as the difference between the sum of the model fitted values (i.e., model predicted number of cases), and the sum of the expected cases (i.e., all observed time is treated as control time). The standard error (SE) of the AR is estimated by bootstrap resampling 10,000 times. For each iteration, this study will sample the beneficiaries with AE with replacement and repeat the AR calculation. The SE is calculated as the square root of the variance of the 10,000 AR values. AR estimates will be reported for each of the AEs for influenza vaccines overall, and by high-dose and adjuvanted vaccine groups separately.

6. Medical Record Review

For AEs without PPVs available from previous medical record review, medical record review may be considered if a significant elevation in incidence rates is detected from the study. The purpose of medical record review will be to evaluate the accuracy of the claims-based outcome definition(s) used. AE-specific PPVs and 95% CIs will be estimated to assess the probability of event misclassification based on the claims-based definitions used.

7. Ethical Evaluation

This public health surveillance activity is conducted as part of the FDA CBER BEST Initiative under the FDA Amendments Act of 2007. This study uses Medicare administrative claims data. The study involves no personal health information; no direct intervention on study participants; data used in this study is de-identified and anonymized before its use; the analysis is conducted in a Federal Information Security Management Act compliant environment; and the results are presented in aggregate.

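### For the three AEs with 42-day risk intervals, the 2021 monthly rates enter the IRR model as if known, so the IRR test and the AR standard error omit their sampling error

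*Protocol*

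**What the plan says.** Protocol Section 5.5.5.1 adjusts the main model for season. "The baseline rate of AEs will be estimated from a similar population during the same calendar months in previous years", and the rates are "subsequently included as an offset term in the regression model". One year supplies them: "For each AE, 2021 will be the comparator year used to adjust for changes in the baseline rate". The model equation contains log(seasonal_risk), built from one "daily incident rate for month" for each calendar month, with no coefficient to estimate and no variance term.

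The decision rule in the same section is "A statistically significant coefficient at a pre-specified alpha level of 0.05". The feasibility step in Section 5.5.1 works "based on the expected sample size at 80% power and a two-sided alpha of 0.05".

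For the GBS example, Section 5.4.1 describes the observation period as "including a 42-day risk interval, and a control interval extending from day 43 to day 90 following vaccination". Table 4 gives the same windows for encephalitis/encephalomyelitis and transverse myelitis.

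The only resampling in the protocol is the AR bootstrap in Section 5.5.6: "this study will sample the beneficiaries with AE with replacement and repeat the AR calculation". It does not mention redrawing the 2021 rates.

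**The concern.** The monthly rates are estimates from counts of rare events in a single year, but an offset treats them as exact. With vaccination between 1 August and 12 November 2022 (Section 4.2) and windows of days 1-42 and 43-90, risk time and control time fall largely in different months. A chance error in, say, the October or December rate of 2021 therefore moves the log IRR directly. People vaccinated at about the same time share nearly the same error, so adding cases does not average it out.

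The size of Medicare does not settle the matter. The AE rate governs both the study counts and the 2021 counts, so a larger database reduces both sources of error together. What counts is how large the 2021 population is relative to the vaccinees.

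At stake is the 0.05 decision. A significant elevation triggers the concomitant-vaccination analysis (Section 5.5.4). For AEs without an existing PPV, which include encephalitis/encephalomyelitis and transverse myelitis, it may also lead to medical record review (Section 6).

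**Working it through.** **Inputs from the protocol.** Windows 1-42 and 43-90 days, and 0-1 and 3-16 days for anaphylaxis (Table 4); vaccination dates 1 August to 12 November 2022 (Section 4.2); one reference year and monthly rates (Section 5.5.5.1); two-sided 0.05 (Sections 5.5.1 and 5.5.5.1).

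**Assumptions, not in the protocol.** R = 2021 reference population / vaccinees, taken as 1, 2 and 5. Three uptake curves: uniform; bell-shaped around 1 October (SD 21 days); bell-shaped around 10 October (SD 14 days). Flat true AE rate, IRR = 1, model-based SE, no Farrington weight and no PPV step.

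**Step 1: the plan's own figure.** The conditional Poisson model was simulated with the offset truly known (6,000 runs). Rejection was 0.0508 with 100 expected cases and 0.0483 with 300. The Monte Carlo SE is √(0.05 × 0.95 / 6000) = 0.0028, so the nominal 0.05 is reproduced.

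**Step 2: the omitted variance.** Let λ be the daily AE rate, N the number of vaccinees and d_m the mean share of risk days minus the mean share of control days in month m.

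- Study variance of log IRR: (1/42 + 1/48) / (Nλ) = 0.04464 / (Nλ)
- Added offset variance: Σ d_m² / (R × Nλ × days_m)
- Inflation: Σ (d_m² / days_m) / (0.04464 × R); Nλ cancels
- True alpha: 2 × [1 − Φ(1.96 / √(1 + inflation))]

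For the 1 October curve, d is about 0.01 (Aug), 0.17 (Sep), 0.40 (Oct), −0.03 (Nov), −0.40 (Dec) and −0.14 (Jan). With these rounded values Σ d_m²/days_m is about 0.0120, and 0.0120/0.0446 is about 0.27. Unrounded, the inflation at R = 1 is 0.2659, so the SE ratio is √1.2659 = 1.125 and alpha is 0.0815.

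**Step 3: range for the AEs with 42-day risk intervals** (SE ratio, then true alpha).

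| Uptake curve | R = 5 | R = 2 | R = 1 |
|---|---|---|---|
| Uniform | 1.011, 0.0526 | 1.028, 0.0565 | 1.055, 0.0632 |
| 1 October, SD 21 | 1.026, 0.0562 | 1.064, 0.0656 | 1.125, 0.0815 |
| 10 October, SD 14 | 1.039, 0.0593 | 1.096, 0.0736 | 1.184, 0.0977 |

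At R = 10 the three curves give alpha 0.0513, 0.0531 and 0.0546.

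**Step 4: anaphylaxis.** Both windows lie within 17 days of vaccination, so the offsets nearly cancel. Even at R = 1 the SE ratio is at most 1.001 and alpha at most 0.0503.

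**Step 5: check by simulation.** The 2021 monthly counts were drawn as Poisson under the 1 October curve. Rejection at R = 5, 2 and 1 was 0.0535, 0.0607 and 0.0812 with 100 expected cases, and 0.0528, 0.0627 and 0.0770 with 300. With 100 cases and R = 2, the empirical SD of log IRR was 0.2161 against a mean model SE of 0.2024, a ratio of 1.068 (delta method 1.064). The similar results for 100 and 300 cases confirm that case numbers do not remove the effect.

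**The case against.** The strongest reply is that the decisive input is absent. The protocol gives no vaccinee count, no size for the 2021 population and no monthly counts; Table 1 gives only more than 34 million enrollees a year for the source. A reader might infer that the test runs at nearly twice its nominal level. That needs both a reference population no larger than the vaccinated cohort and uptake concentrated in October, and the protocol establishes neither. At R = 5 the excess is under one percentage point. This part of the reply stands, which is why only a range is given.

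A reader might also infer that all main intervals are too narrow. Anaphylaxis is a clear exception. The high-dose, adjuvanted and concomitant-vaccination analyses involve fewer vaccinees, so R is larger and the effect smaller if the full 2021 population serves them; the protocol does not say whether it does.

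The calculation also leaves out the Farrington weight and, for GBS, the PPV adjustment, whose estimate has its own uncertainty (63-79% in Table 5). The protocol does not state how the SE of the IRR is obtained, and an SAP may do so. The IRR figures therefore hold only for model-based SEs. The AR bootstrap, however, is fixed in the protocol, and its resampling unit leaves out the 2021 rates.

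The separate model without seasonality (Section 5.5.3.1) does not correct the interval of the main model.

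**Conclusion.** The point holds in a limited form. For GBS, encephalitis/encephalomyelitis and transverse myelitis, the protocol treats one-year estimated rates as known. As written, neither the IRR test nor the AR bootstrap accounts for their sampling error. The direction is certain under model-based SEs: the nominal SE is too small. The amount is not known from the protocol. Over the uptake curves considered, the true SE is about 1-4% above nominal at a population ratio of 5, 3-10% at 2 and 5-18% at 1, with two-sided alpha of 0.053-0.059, 0.057-0.074 and 0.063-0.098. The understatement of the AR SE was not calculated.

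This concerns precision. It does not show a biased IRR, and it says nothing on whether 2021 had the same seasonal pattern as 2022-23, which is a separate question. Severity is minor to moderate: small if the 2021 rates come from a population several times the vaccinees, worth correcting if the two are of similar size.

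**What to change.** In Sections 5.5.5.1 and 5.5.6, state that each bootstrap iteration redraws the 2021 monthly event counts (Poisson) together with the cases, recomputes seasonal_risk and refits the model. Use the result for the IRR interval, the 0.05 decision and the AR SE. Define the 2021 reference population, say whether the same one serves the vaccine-group and concomitant-vaccination analyses, and report its monthly event counts for each AE so that readers can judge the added variance.

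The cost is a few lines of code, a sentence or two in each section and a little more computing. Intervals become slightly wider; point estimates do not change.

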5.5.5.2 Positive Predictive Value (PPV) Adjustment Analysis

For certain AEs with PPVs available from prior medical record review (anaphylaxis and GBS), a PPV-adjustment will be included in the model for both primary and follow-up analyses to ascertain IRR estimates that account for potential outcome misclassification related to the claims-based AE definition. Table 5 presents the PPV estimates that will be used for the adjustment based on medical record review findings from previously published studies using a CMS population. IRRs directly obtained from primary and follow-up analyses without a PPV adjustment may be biased, as a portion of the cases identified during the observation period may not be true cases. PPV-adjusted models will be implemented including the Farrington adjustment only, and in a combined model including both Farrington and seasonality adjustments.

Table 5. AE Positive Predictive Value (PPV) Estimates from Prior Medical Record Review

AE (Setting)	PPV (95% CI)
Anaphylaxis (IP, OP-ED)	66% (95% CI: 56%, 76%) ⁽³⁴⁾
GBS (IP, primary diagnosis position)	71% (95% CI: 63%, 79%) ⁽³⁵⁾

5.5.6 Attributable Risk (AR) Estimation

For the primary analyses and when follow-up analyses apply, the study will also estimate an adjusted AR statistic (per 100,000 vaccinations). The AR is the excess number of AE cases divided by the number of eligible beneficiaries (or eligible follow up dose-years). The number of excess AE cases due to the influenza vaccine will be derived directly from the conditional Poisson regression model, defined as the difference between the sum of the model fitted values (i.e., model predicted number of cases), and the sum of the expected cases (i.e., all observed time is treated as control time). The standard error (SE) of the AR is estimated by bootstrap resampling 10,000 times. For each iteration, this study will sample the beneficiaries with AE with replacement and repeat the AR calculation. The SE is calculated as the square root of the variance of the 10,000 AR values. AR estimates will be reported for each of the AEs for influenza vaccines overall, and by high-dose and adjuvanted vaccine groups separately.

6. Medical Record Review

For AEs without PPVs available from previous medical record review, medical record review may be considered if a significant elevation in incidence rates is detected from the study. The purpose of medical record review will be to evaluate the accuracy of the claims-based outcome definition(s) used. AE-specific PPVs and 95% CIs will be estimated to assess the probability of event misclassification based on the claims-based definitions used.

7. Ethical Evaluation

This public health surveillance activity is conducted as part of the FDA CBER BEST Initiative under the FDA Amendments Act of 2007. This study uses Medicare administrative claims data. The study involves no personal health information; no direct intervention on study participants; data used in this study is de-identified and anonymized before its use; the analysis is conducted in a Federal Information Security Management Act compliant environment; and the results are presented in aggregate.

Using Medicare administrative data for this public health surveillance activity is permitted under the Health Insurance Portability and Accountability Act Privacy Rule for public health practice without individual authorization. Furthermore, public health surveillance activities including this study are not subject to the Common Rule as verified in the Office of Human Research Protections correspondence.⁽³⁶⁾ Therefore, public health surveillance activities within the Sentinel/BEST Initiative are exempt from Institutional Review Board review and approval. In addition, our study practices are performed in accordance with the Declaration of Helsinki guidelines.⁽³⁷⁾

8. Quality Assurance and Control

The analyses described in this protocol will be conducted using Medicare which is a well-characterized administrative claims database, in which the Office of Biostatistics and Pharmacovigilance (OBPV) has previously conducted numerous epidemiologic studies. The current study team will perform quality control measures in the databases such as executing verification checks, examining the validity of claims data variables, evaluating stability of enrollment and health event trends, and assessing consistency with population selection criteria for the database.

9. References

1. Centers for Disease Control and Prevention. 2022-2023 U.S. Flu Season: Preliminary In-Season Burden Estimates 2023 [Available from: <https://www.cdc.gov/flu/about/burden/preliminary-in-season-estimates.htm>].
3. Centers for Disease Control and Prevention. Seasonal Flu Vaccines 2023 [Available from: <https://www.cdc.gov/flu/prevent/flushot.htm#:~:text=For%20the%202022%2D2023%20flu%20season%2C%20there%20are%20three%20flu,Fluad%20Quadrivalent%20adjuvanted%20flu%20vaccine>].
5. Institute for Vaccine Safety JHBoSoPH. Do Vaccines Cause Transverse Myelitis? [Available from: <https://www.vaccinesafety.edu/do-vaccines-cause-transverse-myelitis/>].

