5.1. Study Population

The study will include eligible vaccinees enrolled in Medicare during the study period who receive an influenza vaccine and meet the inclusion and exclusion criteria below, regardless of AE occurrence. All eligible vaccinees will be used to estimate attributable risks (ARs), whereas a subset population with an observed AE occurrence during the observation period (case population) will be used to estimate IRRs.

Inclusion criteria

- (i) Beneficiaries must be enrolled in Medicare Part A (inpatient insurance) and Part B (outpatient and physician services insurance) FFS plans during the observation period, which extends from vaccination date through the earlier of the AE control period end, or any of the censorship criteria (i.e., disenrollment, subsequent influenza vaccination, study period end, or death). Definitions for the risk, control and observation period can be referenced in Section 5.4.
 - If a follow-up concomitant vaccines analysis is applicable, Part D insurance will also be required during the observation period to ensure comprehensive capture of concomitant vaccinations.
- (ii) Beneficiaries must have received an influenza vaccine during the study period and prior to the vaccination cutoff date (latest date vaccine administration will be eligible for inclusion in the study). Further information on the rationale for this cutoff is provided in Section 5.5.1.
- (iii) Beneficiaries will be required to have continuous enrollment in Medicare Parts A and B FFS from 365 days prior to influenza vaccination through the earlier of the observation period end, or any of the censorship criteria (i.e., disenrollment, subsequent influenza vaccination, or death).

- (iv) For the case population only, each case must have a record of an incident AE diagnosis during the observation period.

Exclusion criteria

- (i) Medicare beneficiaries less than 65 years of age at the time of influenza vaccination.
- (ii) Individuals that do not contribute *any* follow-up time to both risk and control intervals i.e. beneficiaries that meet any of the censorship criteria during the risk interval prior to accumulating time in the control interval will be excluded.
- (iii) Individuals vaccinated with multiple influenza vaccine brands on the same day or multiple influenza vaccinations (same/different brand) within 3 days of each other.
- (iv) People who received a diagnosis of the AE during the AE-specific clean period.

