5.5.3 Primary Inferential Analysis

5.5.3.1 Incidence Rate Ratio (IRR) Estimation

The primary inferential analysis will evaluate the incidence rates of AEs following the influenza vaccines, comparing the rates of AEs in the risk and control intervals using a conditional Poisson regression model, conditioning on the total number of AEs observed for an individual patient in the observation period. This analysis will be restricted to the case population and conducted for each AE for influenza vaccines overall and by high-dose and adjuvanted vaccine groups.

The main primary analysis model will include a Farrington, seasonality and positive predictive value (PPV) adjustment (for AEs with PPVs available based on medical record review). The Farrington adjustment will be used to account for the reduced observation time that can occur from the occurrence of an event.⁽²⁷⁾ A separate analysis will be conducted including Farrington and PPV adjustments only, to evaluate the independent effect of the PPV adjustment excluding the seasonality adjustment. Another separate analysis will be performed including Farrington and seasonality adjustments only to evaluate

³ Covariate will be based on Health and Human Service (HHS) Region as specified on <https://www.hhs.gov/about/agencies/iea/regional-offices/region-1/index.html>

⁴ Beneficiaries' immunocompromised status will be determined based on a CBER-modified algorithm adapted from the Greenberg et al. algorithm, which was developed and validated to identify immunocompromised persons. Details on the algorithm can be found in Appendix 10.21.

the independent effect of the seasonality adjustment. The approach for the seasonality and PPV adjustments are specified in Section 5.5.5.

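### The attributable-risk bootstrap resamples only the cases, so its SE omits the random variation in the case count and is too small whenever there is a real excess

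*Protocol*

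**What the plan says.** Section 5.5.6 of the protocol defines the estimand: "The AR is the excess number of AE cases divided by the number of eligible beneficiaries (or eligible follow up dose-years"). The excess is the sum of the model's fitted values minus "the sum of the expected cases (i.e., all observed time is treated as control time").

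The same section then fixes the variance method in three steps.
- Method and number of iterations: "The standard error (SE) of the AR is estimated by bootstrap resampling 10,000 times".
- Unit that is drawn in each of them: "For each iteration, this study will sample the beneficiaries with AE with replacement and repeat the AR calculation".
- Summary taken over the replicates: "The SE is calculated as the square root of the variance of the 10,000 AR values".

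No resample size is stated, and no further variance term is added.

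Two other places bear on this. Section 5.1 separates the populations: "All eligible vaccinees will be used to estimate attributable risks (ARs), whereas a subset population with an observed AE occurrence" is used for the IRR. Section 5.5.3.1 says that the Poisson model works by "conditioning on the total number of AEs observed for an individual patient in the observation period".

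**The concern.** Holding the number of cases fixed suits the IRR, which comes from a conditional model and depends only on how the cases divide between risk and control time. It does not suit the AR. If the same vaccinees had produced 20% more cases with the same split, the IRR would not move, but the excess and the AR would each rise by 20%. A bootstrap that always draws n cases from the n observed never shows that variation.

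The AR is the protocol's absolute measure of harm. It is to be reported for every adverse event, overall and for the high-dose and adjuvanted groups, and again in follow-up analyses, which are run only after a significantly raised rate. The SE is therefore sound where there is no excess and too small where the AR is most likely to be read closely.

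**Working it through.** The protocol states no AR, SE, case count or expected IRR, so there is no figure to reproduce. The check is a closed form followed by a simulation.

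**Inputs**
- Anaphylaxis (Table 4): risk days 0–1 (2 days), control days 3–16 (14 days). Length ratio k = 2/14 = 0.143.
- GBS (section 5.4.1: "including a 42-day risk interval, and a control interval extending from day 43 to day 90 following vaccination"), with the same intervals for encephalitis and transverse myelitis in Table 4: k = 42/48 = 0.875.
- IRR (θ): not given, so a range is assumed.
- The Farrington, seasonality and PPV terms are left out, and follow-up is taken as complete.

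**Excess.** Let a be the cases in the risk interval, b those in the control interval, and n = a + b. The fitted values sum to n. If all time were control time, b + k·b cases would be expected. So excess = n − (1 + k)b = a − k·b.

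**Two variances**
- Case count free to vary (a and b independent Poisson): a + k²b.
- Case bootstrap with n fixed (a binomial given n): (1 + k)²·ab/n.
- Difference: (a + k²b) − (1 + k)²ab/n = (a − k·b)²/n = excess²/n. This is zero only when the excess is zero, and never negative.

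**SE ratio.** With expected risk share p = kθ/(1 + kθ), the ratio of stated to correct SE is the square root of (1 + k)²θ / [(1 + kθ)(θ + k)].
- Anaphylaxis, θ = 10: 64·10/[(7 + 10)(7·10 + 1)] = 640/1207 = 0.530; square root 0.728.
- 42/48 days, θ = 2: 225·2/[(8 + 7·2)(8·2 + 7)] = 450/506 = 0.889; square root 0.943.

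Coverage of an interval of estimate ± 1.96 SE is about 2Φ(1.96 × ratio) − 1.

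| Assumed IRR | Anaphylaxis (2/14): SE ratio | Coverage | 42/48-day events: SE ratio | Coverage |
|---|---|---|---|---|
| 1 | 1.000 | 95% | 1.000 | 95% |
| 1.5 | 0.991 | 95% | 0.980 | 94.5% |
| 2 | 0.974 | 94% | 0.943 | 93.5% |
| 3 | 0.934 | 93% | 0.867 | 91% |
| 5 | 0.861 | 91% | 0.746 | 86% |
| 10 | 0.728 | 85% | 0.576 | 74% |

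Read across a row: at equal IRR the 42/48-day events lose more. Anaphylaxis loses more only if its IRR exceeds about 1.8 when the other event has 1.5, about 2.8 when it has 2, and about 4.8 when it has 3.

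**Simulation** (100 cases expected, 3,000 data sets, 2,000 resamples each)

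| Setting | True SD of excess | Case-only bootstrap SE (coverage) | Case count varying: SE (coverage) |
|---|---|---|---|
| Anaphylaxis, IRR 5 | 6.49 | 5.60 (90.3%) | 6.52 (94.3%) |
| Anaphylaxis, IRR 10 | 7.64 | 5.59 (85.7%) | 7.72 (94.8%) |
| 42/48 days, IRR 2 | 9.43 | 8.97 (93.9%) | 9.56 (95.3%) |

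The simulation agrees with the closed form.

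**The case against.** Several points can be made for the plan as it stands.

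- **The resample size is inferred.** Section 5.5.6 gives none, and section 5.1 says that all eligible vaccinees enter the AR. But 5.5.6 names the cases as the units drawn, and drawing as many as were observed is the usual meaning. Using all vaccinees as the denominator does not make the numerator's case count vary. The point stands on that reading.
- **The loss is small for modest effects.** True: nothing at IRR 1, and 2% or less for the 42/48-day events up to IRR 1.5. It is large only at IRRs that the protocol does not give.
- **Nothing is decided on the AR's SE.** True. The hypothesis test, the trigger for follow-up analyses and the possible medical record review all rest on the incidence rate comparison. This lowers the severity but does not make the SE right.
- **The figures are not for the main model.** True. The main model carries Farrington and seasonality terms, and a PPV adjustment for anaphylaxis and GBS. As described, none of these restores variation in the case count, but they change the ratios. As an illustration only: if the PPV adjustment kept each resampled case with probability 0.66, the variance shortfall for anaphylaxis would be 34% smaller, with SE ratios of about 0.91 at IRR 5 and 0.83 at IRR 10. The defect shrinks but does not vanish.

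Three stronger readings are tempting, and the protocol does not support them:
- A reader might infer that anaphylaxis is the worst case because its risk interval is so short. That holds only if its IRR is sufficiently higher than the others; at equal IRR the order reverses.
- A reader might infer that the Table 5 PPVs enter the AR as constants, so that their uncertainty is lost as well. Section 5.5.5.2 does not say how the adjustment works, and repeating the AR calculation in each iteration could include a PPV draw.
- A reader might infer that the protocol's AR confidence intervals are known to under-cover. Section 5.5.6 defines an SE and no interval, so the coverage figures apply only to an interval built from that SE.

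**Conclusion.** The rule in section 5.5.6 is wrong as written on its standard reading. It treats the case count as fixed for a quantity that depends on it, omits excess²/n from the variance of the excess, and understates the SE whenever the excess is not zero. An SE-based 95% interval would under-cover accordingly: about 91% and 85% for anaphylaxis at IRR 5 and 10.

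These sizes assume a Poisson case count, complete follow-up, IRRs chosen for illustration, and no Farrington, seasonality or PPV terms. The direction of the error does not depend on the IRR chosen. IRR estimates, hypothesis tests and the AR point estimate are unaffected. It should be fixed, but it does not threaten the primary comparison.

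**What to change.** Amend section 5.5.6 so that the number of cases varies between iterations. Any one of these will do:
- in each iteration draw N* from a Poisson distribution with mean n and resample N* cases or, equivalently, give each case an independent Poisson(1) weight;
- resample all eligible vaccinees rather than the cases alone;
- keep the present bootstrap and add excess²/n to the variance of the excess before dividing by the denominator.

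The first needs one sentence in the protocol, almost no code and no new data. The cost is wider AR error bars wherever there is an excess.
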